3. SPECIFIC AIMS

3.1 Overall Study Design and Plan

The study uses a double-blinded, placebo lead-in, randomized, parallel group, PBO-controlled design. For this clinical trial, one-hundred individuals over 17 years of age meeting operationalized criteria for Long-COVID will be recruited. These 100 participants will undergo a placebo lead-in period of two weeks. Sixty participants will then be randomized to NR (TruNiagen®, Chromadex) 1000 mg twice daily for 22 weeks, and 40 will receive placebo for the next 10 weeks followed by NR for 10 weeks. Outcomes will consist of standardized cognitive, neuropsychiatric, physical, functional and biomarker assessments as well as daily sleep and activity monitoring with wearable actigraphy.

Randomized, Placebo-Controlled Parallel Group Clinical Trial of Nicotinamide Riboside to evaluate NAD+ Levels in Individuals with Persistent Cognitive and Physical Symptoms After COVID19 Illness ("Long-COVID")

Version 1.1

The study will also help better understand the nature of long-COVID by comparing this group with a healthy control group of individuals who were infected with COVID-19 but fully recovered. To better address this aim, we will also increase our sample size of individuals with long-COVID by testing individuals with long-COVID ages 18 and older who will only complete 1 visit. Comparing these groups will help establish differences in NAD+ levels at baseline associated with long-COVID, as well as help elucidate the cognitive profile, neuropsychiatric and physical functioning, and markers of glia and neural functioning in this population. Participants in these additional cohorts will only complete one visit and will not be administered NR or PBO.

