4. SUBJECT SELECTION

4.1 Inclusion and Exclusion Criteria

4.1.1 Inclusion Criteria

A subject will be eligible for participation in the **clinical trial** if they meet the following:

- 1. Ages 18 to 65 years;
- 2. History of SARS-CoV-2 PCR+ or COVID-19 Antigen Rapid Self-Test at least 2 months prior to study entry;
- 3. SARS-CoV-2 negative (PCR) at study entry;
- 4. Persistent cognitive difficulties (esp. "brain fog") that began around the time of the acute COVID-19;
- 5. At least two neurological and/or physical symptoms that started at COVID-19 infection and are ongoing at study entry, including fatigue, weakness, headache, loss of smell, tingling/numbness, shortness of breath, loss of appetite, palpitations/tachycardia, hair loss, musculoskeletal and/or chest pain;
- 6. Minimum score of 18 on the MMSE;
- 7. Education level, language skills, and literacy indicates participant is able to complete all assessments;

Randomized, Placebo-Controlled Parallel Group Clinical Trial of Nicotinamide Riboside to evaluate NAD+ Levels in Individuals with Persistent Cognitive and Physical Symptoms After COVID19 Illness ("Long-COVID")
Version 1.1

8. Willing and able to consent, complete all assessment and study procedures.

A subject will be eligible to participate as a **HC Participant** for a one time visit if they meet the following:

- 1. Ages 18 or older;
- 2. History of SARS-CoV-2 PCR+ or COVID-19 Antigen Rapid Self-Test+ at least 2 months prior to study entry;
- 3. SARS-CoV-2 negative (PCR) or COVID-19 Antigen Rapid Self-Test at study entry;
- 4. Experienced full recovery and does not have persistent cognitive difficulties, neurological and/or physical symptoms associated with COVID-19 infection;
- 5. Minimum score of 18 on the MMSE;
- 6. Education level, language skills, and literacy indicates participant is able to complete all assessments;
- 7. Willing and able to consent, complete all assessment and study procedures.

A subject will be eligible to participate as a **long-COVID Participant** for a one time visit if they meet the following:

- 1. Ages 18 or older;
- 2. History of positive SARS-CoV-2 PCR or COVID-19 Antigen Rapid Self-Test at least 2 months prior to study entry;
- 3. Negative COVID-19 Antigen Rapid Self-Test at study entry;
- 4. A minimum score of 18 on the Mini-Mental state examination;
- 5. Report persistent cognitive difficulties ("brain fog") that began around the time of the acute COVID19 illness;

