9.1 Primary analysis

For all outcomes, we will perform intention-to-treat (ITT) analysis and mixed-effects model repeated measures (MMRM). Group (NR-NR vs. PBO-NR sequence), time, and group by time interactions will be included in the MMRM as fixed effects. The study's outcomes will be the change score of ECog, RBANS, and TMT-B from baseline, and the change in NAD+ levels from baseline. We also will examine changes in the FSS, BAI, BDI, and PSQI scores. An unstructured covariance matrix will be used to account for the correlation of repeated measures within a participant. Age, sex, and education will be included in the models as covariates.

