9.1.2 Post-Hoc Analysis

The sequential block design will provide the opportunity to examine the effects of NR using a larger sample size, as all participants will ultimately receive 10 weeks of NR (baseline to visit 2 for the NR-NR group; visits 2–4 for the PBO-NR group). In addition to the standard MMRM analysis, we will combine the data from the two randomized groups and explore the pre-post changes in outcomes after 5 and 10 weeks of NR intake compared to baseline. To explore the potential impact of NAD+ levels on change in outcomes, we will perform linear regression analyses of change scores and NAD+ levels measured after 10 weeks, controlling for age, sex, education, and time since acute COVID-19 infection.

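### Time since acute COVID-19 is adjusted for in the exploratory NAD+ regression but not in the primary MMRM; adding it would be a cheap, optional gain in precision

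*Combined protocol and SAP*

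**What the plan says.** Section 9.1 defines the primary model: "Group (NR-NR vs. PBO-NR sequence), time, and group by time interactions will be included in the MMRM as fixed effects". The covariates follow: "Age, sex, and education will be included in the models as covariates". The outcomes named first are changes from baseline: "The study's outcomes will be the change score of ECog, RBANS, and TMT-B from baseline, and the change in NAD+ levels from baseline". Changes in FSS, BAI, BDI and PSQI are examined as well.

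Section 9.1.2 adds an exploratory analysis: "To explore the potential impact of NAD+ levels on change in outcomes, we will perform linear regression analyses of change scores and NAD+ levels", with NAD+ taken after 10 weeks and "controlling for age, sex, education, and time since acute COVID-19 infection". The plan gives no reason for the different covariate lists.

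Four other places bear on the point:

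- Section 4.1.1 requires, for the clinical trial, a positive test "at least 2 months prior to study entry" and sets no upper limit.
- Section 5.3 assigns randomization to the hospital's clinical trials pharmacy and describes no stratification.
- Sections 6.1 and 7.1 provide for COVID-19 history, which is taken at screening.
- Section 3.1 gives the arm sizes: "Sixty participants will then be randomized to NR", while "40 will receive placebo for the next 10 weeks followed by NR for 10 weeks".

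**The concern.** The outcomes are change scores in a condition that may improve with time, and eligibility permits a wide spread of time since infection. If people with recent infections change at a different rate from people with old ones, time since infection explains part of the variation in change. Left out of the model, that part stays in the residual.

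Section 9.1.2 suggests that the authors see such a link as plausible. A variable can confound a regression of change on NAD+ only if it is related to change as well as to NAD+, and the primary analysis also models change scores.

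At stake is precision in the placebo-controlled comparison. The placebo arm moves to NR after 10 weeks, and the cognitive battery is given only at Weeks 2, 12 and 22 (sections 6.1 and 6.2.3). For RBANS and TMT-B, that comparison therefore rests on one post-baseline visit, Week 12, with 60 against 40 people.

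**Working it through.** The plan states no figure to reproduce: section 9 gives no alpha, power, effect size or SD. The calculation therefore asks what adding the covariate would do at one visit.

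**Inputs from the documents.** Arms of 60 and 40, so N = 100. The existing model at one visit has k = 5 parameters (intercept, group, age, sex, education).

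**Assumptions, not in the documents.** The partial correlation ρ of time since infection with change, given age, sex and education, is varied from 0 to 0.4. For power, two-sided alpha is 0.05 and the true effect is 0.5 SD.

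**Variance of the treatment effect.** Adding one covariate multiplies it by about

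f = (1 − ρ²) × (N − k − 2)/(N − k − 3) = (1 − ρ²) × 93/92.

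The ratio 93/92 is the price of one more estimated parameter. The change in effective sample size is 1/f − 1. Power is Φ(0.5/(0.204 × √f) − 1.96), where 0.204 = √(1/60 + 1/40). Without the covariate it is 68.8%.

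| Assumed ρ | f | Effective N | Power at 0.5 SD |
|---|---|---|---|
| 0 | 1.011 | −1.1% | 68.3% |
| 0.1 | 1.001 | −0.1% | 68.7% |
| 0.2 | 0.970 | +3.0% | 70.1% |
| 0.3 | 0.920 | +8.7% | 72.4% |
| 0.4 | 0.849 | +17.8% | 75.7% |

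**Break-even.** f = 1 when ρ² = 1/93, so ρ is about 0.10. Below that, adjustment costs slightly more than it returns.

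**With attrition.** For 80 evaluable at 3:2 (assumed), the ratio becomes 73/72. The changes are −1.4%, −0.4%, +2.7%, +8.4% and +17.4%, and break-even is about 0.12.

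**Chance imbalance.** Under simple randomization, the standardized arm difference in any baseline variable has SE 0.204. It exceeds 0.2 SD in either direction in 33% of randomizations and 0.4 SD in 5%. At ρ = 0.3, a 0.4 SD imbalance moves the estimate that omits the covariate by 0.3 × 0.4 = 0.12 SD.

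**Validity check.** In a single-visit simulation at 60 and 40 (10,000 runs per setting, ρ from 0 to 0.5), both models were unbiased. Type I error was 4.6% to 5.0% without the covariate and 4.5% to 5.0% with it. At ρ = 0.3 and a 0.5 SD effect, simulated power rose from 66.6% to 69.7%.

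**The case against.** The strongest reply is that the two analyses ask different questions. Section 9.1.2 relates change to a post-baseline NAD+ level that was not randomized, so adjustment there guards against confounding. Section 9.1 compares randomized groups, where the design handles confounding by baseline variables. This stands. A reader might infer that the plan treats the variable as necessary and that the MMRM is therefore inconsistent or biased; the documents support neither. What survives is narrower: listing the variable as a potential confounder of change implies that it may predict change, and that is a good reason to adjust a randomized comparison for it.

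Three further objections also hold:

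- Chance imbalance is not a second harm on top of lost precision. The standard error of the model without the covariate already allows for it, and the 0.12 SD shift needs an uncommon imbalance together with an assumed correlation.
- The change is not free, and its benefit is not assured. The simple formula 100/(1 − ρ²) suggests 101 participants at ρ = 0.1, but once the extra parameter is counted there is no gain.
- The documents do not say that an exact infection date is recorded for everyone, which infection counts after reinfection, or how widely enrolled participants will vary. The eligibility check implies that some timing is known, so missing values should be few, but that is an inference.

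**Conclusion.** A minor, optional improvement. The primary MMRM as written is valid. It forgoes a baseline covariate that the plan uses elsewhere for the same kind of outcome and that should be derivable from history already collected.

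The benefit depends wholly on an unknown partial correlation. It is absent or slightly negative below about 0.10. At an assumed effect of 0.5 SD, it is worth about 1 to 4 power points at 0.2 to 0.3 and about 7 points at 0.4. The worst case is a loss of about 1% in effective sample size. These figures assume a single visit with 60 and 40 evaluable participants.

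**What to change.** In section 9.1, add time since acute COVID-19 infection to age, sex and education as a pre-specified baseline covariate in the MMRM for the clinical outcomes: ECog, RBANS, TMT-B, FSS, BAI, BDI and PSQI. The argument about recovery over time does not clearly extend to change in NAD+, so that model can be left as it is. The functional form (a log scale, for example) and any interaction with visit are optional, but should be settled in advance if used.

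State how the infection date is derived, which infection counts when there was more than one, and how an uncertain or missing date is handled. If the authors prefer to leave the covariate out, one sentence saying why it belongs only in section 9.1.2 would close the point.

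Make the change before treatment codes are released under section 9.1.3. Adding the covariate after an imbalance has been seen would be a data-driven change to the primary model. The cost is a few lines of text, one degree of freedom (more with a visit interaction), and the work of deriving one date per participant.

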9.1.2 Post-Hoc Analysis

The sequential block design will provide the opportunity to examine the effects of NR using a larger sample size, as all participants will ultimately receive 10 weeks of NR (baseline to visit 2 for the NR-NR group; visits 2–4 for the PBO-NR group). In addition to the standard MMRM analysis, we will combine the data from the two randomized groups and explore the pre-post changes in outcomes after 5 and 10 weeks of NR intake compared to baseline. To explore the potential impact of NAD+ levels on change in outcomes, we will perform linear regression analyses of change scores and NAD+ levels measured after 10 weeks, controlling for age, sex, education, and time since acute COVID-19 infection.

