6.2.2 Baseline Visit (Week 2)

The following procedures will be performed and will take approximately 4-5 hours depending on participation in the MRI sub-study. If the subject has elected to participate in the MRI sub-study, the visit may occur over multiple days as long as all tasks are completed during the study visit window.

- Measure Vital Signs
- Blood draw and a collect dried blood spot sample for biomarker analysis
- Assess study supplement compliance
- Assess COVID-19 related symptoms
- Administer cognitive assessments
- Administer questionnaires about neuropsychiatric symptoms, sleep, physical activity and others
- Assess and document AEs and changes to medical history¹
- Review and document concomitant medications, supplements, and therapies¹
- Dispense study supplement or PBO¹
- Perform optional MRI scan
- Reassess inclusion and exclusion criteria¹

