6.2.3 Follow Up Visits (Weeks 7, 12 and 17)

These visits will take place every 5 weeks (± 2 days) following Baseline.

Randomized, Placebo-Controlled Parallel Group Clinical Trial of Nicotinamide Riboside to evaluate NAD+ Levels in Individuals with Persistent Cognitive and Physical Symptoms After COVID19 Illness ("Long-COVID")
Version 1.1

¹These procedures can take place virtually via Zoom videoconference if necessary.

- Review and document concomitant medications, supplements, and therapies¹
- Assess COVID-19 related symptoms
- Perform physical assessments
- Perform physical and neurological examination
- Measure vital signs
- Dispense study supplement or PBO¹
- Assess study supplement compliance
- Administer battery of cognitive assessments (only week 12)
- Administer questionnaires about neuropsychiatric symptoms, sleep, physical activity and others
- Blood draw and a collect dried blood spot sample for biomarker analysis
- Assess and document adverse events (AEs) and changes to medical history¹

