6.2.4 Final study visit

This visit will take place at Week 22.

- Measure Vital Signs
- Perform physical and neurological examination
- Blood draw and a collect dried blood spot sample for biomarker analysis
- Assess study supplement compliance
- Assess COVID-19 related symptoms
- Administer cognitive assessments
- Administer questionnaires about neuropsychiatric symptoms, sleep, physical activity and others
- Assess and document AEs and changes to medical history¹
- Review and document concomitant medications, supplements, and therapies¹
- Perform physical assessments
- Perform optional MRI scan

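### The exploratory pooled NR analysis (9.1.2) names baseline as its reference, which conflicts with the Week 12–22 exposure window it gives for the placebo-first group

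*Combined protocol and SAP*

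**What the plan says.** Section 9.1.2 (Post-Hoc Analysis) justifies pooling by noting that "all participants will ultimately receive 10 weeks of NR", and gives the exposure windows as "baseline to visit 2 for the NR-NR group; visits 2–4 for the PBO-NR group". The next sentence combines the two groups to "explore the pre-post changes in outcomes after 5 and 10 weeks of NR intake compared to baseline". It gives no separate reference for the placebo-first group. A further sentence plans a linear regression of change scores on NAD+ measured after 10 weeks. It does not say which visit the change is taken from, or from which visit the 10 weeks are counted.

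Elsewhere in the same document:

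- Section 6.2.2 places the Baseline visit at Week 2. Figure 4 (5.3) and the table in 6.1 put Visits 1 to 4 at Weeks 7, 12, 17 and 22. Section 6.2.4 confirms the last of these: "This visit will take place at Week 22".
- Section 3.1 randomizes 60 participants to NR from the start. For the others, "40 will receive placebo for the next 10 weeks followed by NR for 10 weeks".
- Section 9.1 takes change from baseline for ECog, RBANS, TMT-B and NAD+. For FSS, BAI, BDI and PSQI it refers to changes without naming a reference.
- Among the follow-up visits, the cognitive tests are given at one only (6.2.3: "Administer battery of cognitive assessments (only week 12"). With Week 2 and Week 22, that makes three administrations.

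**The concern.** The sentence on exposure windows uses the word baseline for the Week 2 visit, since that is where NR starts in the NR-NR group. The sentence that defines the change score then uses the same word for both groups. In the PBO-NR group Week 2 is the start of placebo, not of NR. Subtracting the Week 2 value there gives a score that mixes 10 weeks of placebo with 5 or 10 weeks of NR, and pools it with NR-NR scores that contain NR time only.

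Placebo response, practice gain or natural recovery during Weeks 2 to 12 would then be reported as change on NR, in the analysis that the protocol offers as its larger-sample look at NR. Two analysts could follow the section in good faith and report different numbers. Under 9.1.3 the treatment codes are released before the analysis is run, so an open choice of reference could be settled with allocation known.

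**Working it through.** **Inputs.** Baseline is Week 2 (6.2.2). Visits 1, 2, 3 and 4 are at Weeks 7, 12, 17 and 22 (5.3, 6.1). Group sizes are 60 NR-NR and 40 PBO-NR (3.1). The documents give no figure for change during the placebo period, so d below is an assumption, in SD units of the outcome.

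**Step 1: the plan's own 10-week figure.** NR-NR: 12 − 2 = 10 weeks. PBO-NR: 22 − 12 = 10 weeks. The exposure windows in 9.1.2 therefore reproduce the stated 10 weeks of NR in both groups, with no placebo time in either.

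**Step 2: the change scores under each reference.**

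| Group and reference | 5 weeks of NR | 10 weeks of NR | Placebo weeks included |
|---|---|---|---|
| NR-NR, Week 2 | 7 − 2 = 5 weeks | 12 − 2 = 10 weeks | 0 |
| PBO-NR, Week 2 (stated reference) | 17 − 2 = 15 weeks | 22 − 2 = 20 weeks | 10 |
| PBO-NR, Week 12 (exposure window) | 17 − 12 = 5 weeks | 22 − 12 = 10 weeks | 0 |

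Under the stated reference, placebo makes up 10/15 = 67% of the PBO-NR span for the 5-week score and 10/20 = 50% for the 10-week score.

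**Step 3: effect on the pooled mean.** Let m1 be the mean change on NR in NR-NR, m2 the mean change on NR in PBO-NR, and d the mean change in PBO-NR from Week 2 to Week 12. For a simple mean over 100 participants:

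- Week 12 reference for PBO-NR: 0.6·m1 + 0.4·m2
- Week 2 reference for PBO-NR: 0.6·m1 + 0.4·(m2 + d)
- Difference: 0.4·d, the same for the 5- and 10-week scores

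| Assumed d (SD) | 0 | 0.1 | 0.2 | 0.3 |
|---|---|---|---|---|
| Shift in pooled mean (SD) | 0 | 0.04 | 0.08 | 0.12 |

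A negative d gives a shift of the same size in the other direction.

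**Step 4: check with a worked case.** Assume NR does nothing and every score drifts linearly by g per 10 weeks. At 10 weeks the pooled change is 0.6g + 0.4(2g) = 1.4g with the Week 2 reference, against g with the Week 12 reference. At 5 weeks it is 0.6(0.5g) + 0.4(1.5g) = 0.9g, against 0.5g. Both differences are 0.4g, which agrees with Step 3 when d = g.

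**Step 5: the regression.** In PBO-NR, 10 weeks counted from baseline is Week 12, the end of placebo. Ten weeks of NR is Week 22. The sentence allows either, so the same conflict carries over.

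**Step 6: are the data there?** The cognitive battery, ECog, the mood and sleep questionnaires and the biomarker blood draw are all scheduled at Week 12, so a pre-NR value exists for PBO-NR. RBANS and TMT-B are collected at Weeks 2, 12 and 22 only. They have no 5-week value in either group, whichever reference is used.

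**The case against.** The best defence is the exposure window itself. It sits one sentence earlier, covers exactly 10 weeks of NR in PBO-NR and excludes placebo. A pre-post change over a stated window naturally starts where the window starts, so a careful statistician would probably use Week 12. The word baseline is also not perfectly uniform, since 7.1.2.5 attaches it to Week 0 for the MRI. All of this stands as evidence of intent. It does not remove the conflict: the window says when NR is taken, while the sentence that defines the change score names a different visit for one of the two groups.

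A reader might infer that the plan definitely uses the wrong visit for all 40 PBO-NR participants. The documents do not support that, because the section points both ways. Nor do they support a claim that the estimate must be inflated: no placebo-period change is given, and its sign could go either way.

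A reader might also want to express this as a false-positive rate. With an assumed linear drift of 0.2 SD per 10 weeks, within-person correlation of 0.7 and no NR effect, a simulated one-sample test on the pooled 10-week change is significant in about 73% of trials with the Week 12 reference and about 95% with Week 2. Most of the 95% therefore comes from having no control group, not from the reference visit, and 9.1.2 names no such test. The shift of 0.4d is the part that belongs to this point.

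The absence of 5-week RBANS and TMT-B values is a matter of wording. It changes no result.

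**Conclusion.** In 9.1.2 the stated reference contradicts the exposure window beside it. Followed as written, it puts 10 placebo weeks into the NR change of 40 of the 100 pooled participants and moves the pooled mean by 0.4d, or 0.04 to 0.12 SD if d is 0.1 to 0.3 SD. This assumes a simple mean over all 100 participants at the planned 60/40 split. The range for d is illustrative.

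The consequence is limited. The analysis is labelled post hoc, is exploratory and is additional to the MMRM. The randomized comparison in 9.1 takes both groups' change from the same Week 2 visit and is untouched. The section is still worth correcting before unblinding, because the correction is small and the pooled result will be presented as change on NR.

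**What to change.** In 9.1.2, replace the reference to baseline in the pooled pre-post sentence with: *compared to the last assessment before the first NR dose (Week 2 for NR-NR; Visit 2, Week 12, for PBO-NR)*. The changes are then Weeks 7 and 12 minus Week 2 for NR-NR, and Weeks 17 and 22 minus Week 12 for PBO-NR.

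Use the same reference for the change scores in the NAD+ regression, and state that the 10-week NAD+ value is the Week 12 sample for NR-NR and the Week 22 sample for PBO-NR. Add that RBANS and TMT-B allow a 10-week change only.

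The cost is a few clauses in one section, with no new visits or data. Two limits remain and should be stated with the result. It is still an uncontrolled pre-post comparison. The cognitive changes are also not matched for practice: PBO-NR would run from the second to the third test administration, and NR-NR from the first to the second.

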2.1.4 Pharmacokinetics of Nicotinamide Riboside in Humans

An open-label, non-randomized study of the pharmacokinetics of NR carried out at the University of Washington demonstrated both the impact of NR on NAD⁺ levels in humans and its tolerability¹⁶. Eight subjects underwent dose escalation from 250 mg of NR twice daily to 1000 mg of NR twice daily over the course of nine days, with NR and NAD⁺ levels determined at baseline Day 1 and over the course of a 24-hour pharmacokinetic study on Day 9. No adverse events were reported in clinical laboratory values, including potassium, which had been noted to be elevated in previous NR studies. Slight, but significant decreases in hematocrit, hemoglobin, and platelet count were reported. All but one subject showed an increase in blood NR levels from baseline to Day 9, ranging from 10% to 127% increases. Blood NR showed exponential decline from 3 to 12 hours with a half-life of 2.7 hours. Despite relatively fast clearance of NR, blood NAD⁺ levels were significantly increased to steady state (see Figure 3) by 35 to 168% from baseline. NR treatment did not produce side effects commonly seen in niacin treatment, such as flushing, pruritus, hyperglycemia, hyperuricemia, or elevation of liver or muscle enzymes. However, a variability in NR bioavailability was observed, suggesting that NR relies on active transport across intestinal mucosa, which can vary highly from person to person.

Randomized, Placebo-Controlled Parallel Group Clinical Trial of Nicotinamide Riboside to evaluate NAD+ Levels in Individuals with Persistent Cognitive and Physical Symptoms After COVID19 Illness ("Long-COVID")

Version 1.1

[figure not shown]

Figure 3. Blood NR and NAD⁺ levels in n = 8 subjects following NR dose escalation from 250 to 1000 mg twice daily.⁶

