3.2.1 Standardized Cognitive, Functional, and Neuropsychiatric Outcome Measures

The primary outcome of this study will be objective measures of cognitive performance and subjective cognitive concerns measured with the following tests:

O The Mini-Mental State Examination (MMSE)²², Wechsler Adult Intelligence Scale-Fourth Edition (WAIS-IV) Digit Span backwards²³, Repeatable Battery for the Assessment of Neuropsychological Status (RBANS)²⁴, the Trail Making Test (TMT)²⁵, the Delis-Kaplan Executive Function System (DKEFS) Verbal Fluency²⁶, and the Continuous Performance Test (CPT). ²⁷ Subjective ratings of everyday cognitive functioning will be measured using items from the Behavior Rating Inventory of Executive Function (BRIEF-A)²⁸ at week 2, week 12 and week 22, and the Everyday Cognition scale (ECog)²⁹ will be measured at each visit.

The secondary and tertiary clinical and exploratory biomarker outcomes of this study will be:

• Assessment of neuropsychiatric symptoms as measured by:

Randomized, Placebo-Controlled Parallel Group Clinical Trial of Nicotinamide Riboside to evaluate NAD+ Levels in Individuals with Persistent Cognitive and Physical Symptoms After COVID19 Illness ("Long-COVID")

Version 1.1

- o Ratings of mood and anxiety will be measured using the Post Traumatic Stress Disorder Checklist-Civilian (PCL-C)³⁰, Beck Anxiety Inventory (BAI)³¹ and Beck Depression Inventory (BDI)³². These standard measures will be administered at each visit.
- Assessment of physical functioning as measured by:
 - o The Fatigue Severity Scale³³.
 - Objective daily physical activity levels and sleep data collected using wrist actigraphy (Fitbit Charge 4).
 - Subjective sleep ratings (Pittsburgh Sleep Quality Index)³⁴ and physical activity (International Physical Activity Questionnaire [IPAQ])³⁵ measures will be collected using questionnaires at each visit.
- Safety and tolerability will be assessed with adverse event (AE) reporting conducted at every visit.
- Plasma for biomarkers will be collected at Week 2, and at every 5 weeks until the end-of-study, and at the one-time visit for HC and long-covid participants. Plasma biomarkers assays will consist of ultrasensitive immunochemical measures of proteins reflecting neurodegeneration/neural injury (e.g. NfL, IL-6 and GFAP), as well as NAD+/NADH).
- Cerebral neurophysiology will be measured with functional MRI (optional sub-study).

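### The exploratory NAD+ regression in 9.1.2 uses the attained NAD+ level without the pre-NR NAD+ or pre-NR outcome value, so its slope does not isolate the association with the NAD+ rise on NR

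*Combined protocol and SAP*

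**What the plan says.** Section 9.1.2 gives the purpose as "To explore the potential impact of NAD+ levels on change in outcomes" and the method as "linear regression analyses of change scores and NAD+ levels measured after 10 weeks, controlling for age, sex, education, and time since acute COVID-19 infection". Those four covariates are the whole list. Pre-NR NAD+, the pre-NR value of the outcome and randomized sequence do not appear.

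The same section pools the two sequences for its pre-post analysis of change on NR. It gives the NR window as "baseline to visit 2 for the NR-NR group; visits 2–4 for the PBO-NR group", which is Weeks 2 to 12 and Weeks 12 to 22 on the visit schedule in 6.1. It does not say whether the 10-week NAD+ measurement means 10 weeks of NR in each sequence or one common study week. Nor does it say from which visit the regression's change scores are taken in the PBO-NR group.

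Section 9.1 handles NAD+ differently. The outcome there is "the change in NAD+ levels from baseline", and "Group (NR-NR vs. PBO-NR sequence), time, and group by time interactions will be included in the MMRM as fixed effects". Sampling supports a pre-NR value in both sequences: "Plasma for biomarkers will be collected at Week 2, and at every 5 weeks until the end-of-study" (3.2.1).

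**The concern.** This is the only planned analysis that links NAD+ to clinical outcome, in a trial whose title names NAD+ levels. Readers will be inclined to take its slope as evidence on whether people whose NAD+ rose more on NR also improved more.

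A single post-treatment level cannot separate someone who began high from someone who responded strongly. Section 2.1.4 itself says "However, a variability in NR bioavailability was observed" and reports NAD+ increases from 35% to 168%. Differences in response are therefore expected, and they are the quantity of interest.

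Two errors are possible. A real association with the rise is diluted by pre-existing NAD+ differences. In addition, if pre-NR NAD+ is related to how impaired a person is at the start, regression to the mean in the outcome produces a slope even when the rise is irrelevant.

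**Working it through.** The plan states no power, alpha or effect size for this regression, so there is no figure to reproduce. The check concerns what the slope estimates.

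**Inputs**
- Allocation 60 NR-NR and 40 PBO-NR (3.1).
- Mean NAD+ rise 60% of baseline (2.1.5); range 35 to 168% in eight subjects (2.1.4).
- SD of the rise, from the range of eight values (expected range 2.847 SDs under normality): (1.68 − 0.35)/2.847 = 0.467 of mean baseline; variance 0.218.
- Baseline NAD+ CV: not in the documents; assumed 0.15 to 0.60.
- Two-sided alpha 0.05: assumed.

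**Dilution.** Write level = B + R, with B the pre-NR value and R the rise. If outcome change depends on R with slope β, and B and R are uncorrelated, the slope on the level is β × Var(R)/[Var(R) + Var(B)]. The correlation of level with rise is the square root of that ratio. Power below is for a true correlation of 0.30 with the rise (Fisher z, N = 100, four covariates). Analysing the rise itself gives 85%.

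| Assumed baseline CV | Level-only slope / slope on rise | Correlation of level and rise | Power using level |
|---|---|---|---|
| 0.15 | 0.218/(0.218 + 0.0225) = 0.91 | 0.95 | 81% |
| 0.30 | 0.218/(0.218 + 0.090) = 0.71 | 0.84 | 70% |
| 0.45 | 0.218/(0.218 + 0.2025) = 0.52 | 0.72 | 56% |
| 0.60 | 0.218/(0.218 + 0.360) = 0.38 | 0.61 | 44% |

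The size depends on scale. On a log scale the SD of the rise is [ln(2.68) − ln(1.35)]/2.847 = 0.241 (variance 0.058), and a baseline CV of c gives variance ln(1 + c²). The ratio is then 0.058/(0.058 + 0.022) = 0.72 at CV 0.15 and 0.058/(0.058 + 0.308) = 0.16 at CV 0.60, so dilution is heavier.

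**Spurious slope.** Suppose the rise has no effect, pre-NR NAD+ correlates 0.4 with the baseline outcome, and the outcome change contains −0.5 per SD of that baseline (both assumed). The expected slope on the level is −0.5 × 0.4 × CV/(0.218 + CV²). At CV 0.30 this is −0.060/0.308 = −0.19; simulation gave −0.20. In 1,500 simulated trials per setting (60:40, without the four demographic and time covariates), the level-only model rejected 10%, 21% and 38% of the time at CV 0.15, 0.30 and 0.60. Adding pre-NR NAD+ and pre-NR outcome gave 5%, 6% and 6%. Pre-NR NAD+ alone already gave about 6%, so it is the more important omission.

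**Sequence, under the two readings of the 10-week point** (simulated at CV 0.30)
- Everyone measured after 10 weeks of NR, with a 0.5 SD shift between sequences: level-only rejection 6%, so no bias in the NAD+ slope.
- Study Week 12 for everyone, so 60 on NR and 40 on placebo, with a 0.5 SD NR effect that does not act through NAD+: level-only rejection 24%, still 32% with pre-NR NAD+ and pre-NR outcome added, and 5% once sequence is added.

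**The case against.** The analysis is labelled post hoc and exploratory, and its stated aim speaks of levels. Whether attained level or rise is the relevant exposure is partly a scientific choice, and no primary or secondary conclusion rests on this model. NAD+ change from baseline is analysed in the MMRM, so the Week 2 value is not ignored overall. All of this stands and limits the weight of the point. It does not make the slope interpretable as the association with the rise.

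A reader might infer that the regression can show nothing about NAD+ response. The documents do not support that. The defect is dilution and possible confounding; with a small baseline spread the level tracks the rise closely (correlation 0.95 at CV 0.15).

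A reader might also infer that leaving out sequence lets calendar time and practice distort the slope, because PBO-NR reaches 10 weeks of NR at Week 22. On that reading everyone has had 10 weeks of NR and sequence was randomized, so sequence is unrelated to NAD+ level in expectation. Omitting it costs precision but does not bias the slope. Sequence confounds only if study Week 12 is used for both groups. Pooling in the regression is itself an inference, since the sentence on combining groups governs the pre-post analysis. ECog is given at every visit, so a practice argument based on the Weeks 2, 12 and 22 battery would not carry over to it.

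Finally, the false-signal mechanism needs pre-NR NAD+ to be related to the baseline outcome. The documents give no evidence either way.

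**Conclusion.** The point holds in a limited form. As specified, the slope in 9.1.2 mixes pre-existing NAD+ with the rise on NR and does not isolate the latter. This follows from the model and needs no assumed number.

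Its size does rest on assumptions. On the additive scale the level-only slope is about 91% to 38% of the slope on the rise for a baseline CV of 0.15 to 0.60. This takes an SD of the rise from the range of eight subjects and assumes that rise and pre-NR level are uncorrelated. The false-positive figures are conditional illustrations, not predictions.

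The undefined 10-week point is a separate ambiguity. It decides whether sequence is a precision term or a necessary confounder adjustment. This is a worthwhile correction to an exploratory analysis and no threat to the primary MMRM.

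**What to change.** In 9.1.2:

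1. State that the 10-week measurement means 10 weeks of NR in each sequence: Week 12 for NR-NR and Week 22 for PBO-NR.
2. Regress change in outcome on change in log NAD+, both from the pre-NR visit: Week 2 for NR-NR and Week 12 for PBO-NR.
3. Adjust for pre-NR NAD+ and pre-NR outcome in addition to the four listed covariates.
4. Include sequence group. Under item 1 it gains precision; if study Week 12 were used for everyone, it would be essential to avoid confounding.
5. Describe the result as an association. The NAD+ rise is not randomized, so even the adjusted model is not proof of mediation.

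The cost is SAP wording and three extra model terms. Blood sampling at Weeks 2, 7, 12, 17 and 22 and the cognitive battery at Weeks 2, 12 and 22 already supply the values. With about 100 participants three terms are affordable. Under the Week 12 reading the sequence term would be dearer: with a true effect of the rise, simulated power fell from 80% to 58%, which is another reason to adopt item 1. The change should be made before the unblinding described in 9.1.3, so that it remains prespecified.
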